#### **9.4.1.5 Concomitant Medication**

**Concomitant medication** - the following will be documented:

- Concomitant medication used from the time when the decision is made to initiate treatment with the ABBVIE REGIMEN until after the last dose

It should be verified by the treating physician that concomitant medication can be safely administered with the ABBVIE REGIMEN (including ritonavir) and RBV. Some medications may be contra-indicated, some may require dose adjustments due to potential for drug-drug interactions (DDIs). The investigator or qualified designee should review the concomitant medication(s) labels and screen concomitant medications at each visit for potential DDIs.

#### **9.4.1.6 Standardized Assessment Tools**

This study will assess quality of life and work productivity using PRO instruments: EQ-5D-5L and WPAI Hep C. Validated translations of these patient questionnaires will be administered.

##### Assessment of general quality of life - EQ-5D-5L

The EQ-5D-5L is a health state utility instrument that evaluates preference for health status (utility). The 5 items in the EQ-5D-5L comprise 5 dimensions (mobility, self-care, usual activities, pain/discomfort, and anxiety/depression) each of which are rated on 5 levels of severity. Responses to the 5 items encode a discrete health state which is

Confidential Information

No use or disclose outside AbbVie is permitted without prior written authorization from AbbVie

The Netherlands v 1.4 (26 March 2018). Protocol based on AbbVie shell protocol version 3.0 (22 April 2015) Page 31 of 65

mapped to a preference (utility) specific for different societies. Patients also rate their perception of their overall health on a separate visual analogue scale (VAS).

The EQ-5D-5L should require approximately 5 minutes to complete and is presented in Annex 2.

#### Assessment of work productivity and activity impairment – WPAI Hep C V2.0

The WPAI questionnaire will be used to measure work absenteeism, work presenteeism, and daily activity impairment. The WPAI questionnaire was created as a patient-reported quantitative assessment of both reduced productivity at work and non-work activities. WPAI has been validated as a general health measure (WPAI-GH) and can be easily modified for specific health condition, disease or problem (WPAI-SHP). WPAI Hep C V2.0 is the HCV specific questionnaire that will be used in this study). Respondents are asked about time missed from work and time while at work during which productivity was impaired in the past seven days. Results of WPAI are expressed as a percentage of impairment from 0 to 100, with higher percentages indicating greater impairment and less productivity:

- % Presenteeism – percentage of impairment while working due to health problem
- % Absenteeism – percentage of work time missed due to health problem
- % Total work productivity impairment (TWP) – percentage of overall work impairment due to health problem
- % Total activity impairment (TAI) – percentage of general (non-work) activity impairment due to health problem

The WPAI Hep C should require approximately 5 minutes to complete and is presented in Annex 3.

PRO data are not considered a potential source of adverse reactions. However, participating sites should review the PRO data and if a possible product-related event (including a suspected adverse reaction) is noted, the health care provider (HCP) must determine whether the event is related to paritaprevir/r – ombitasvir ± dasabuvir (or any other AbbVie authorized product) and if so, it should be reported to AbbVie. The relevant AbbVie Pharmacovigilance contact details are specified in Section 11.0.

---

## **9.5 Study Size**

The sample size of the study is not based on statistical considerations. It is expected that 50-55 patients can be enrolled.

## **9.6 Data Management**

### **9.6.1 Electronic Case Report Forms**

Data for this study will be recorded in English by each participating center via an electronic data capture (EDC) system using a web-based eCRF. Examinations, diagnostic measures, laboratory assessments, findings and observations routinely performed in patients with CHC included in this cohort, will be transcribed by the investigator or designee from the source documents into the eCRF. Only data specified in the protocol will be entered into the eCRF. For each enrolled patient, the investigator or designee will create a new patient file in the eCRF and a unique patient number will be automatically allocated by the system.

A comprehensive data validation program utilizing front-end checks in the eCRF will validate the data. Automated checks for data consistency will be implemented; discrepancies need to be solved by the researcher in the eCRF before the module can be completed.

Follow-up on eCRF data for medical plausibility will be done by AbbVie personnel (or their representatives). Queries will be generated in the eCRF for online resolution at the site. The investigator or an authorized member of the investigator's staff will make any necessary data corrections to the eCRF. All change information, including the date and person performing the corrections, will be available via the audit trail, which is part of the EDC system. The principal investigator of each site will finally review the eCRFs for completeness and accuracy of available data and provide his or her electronic signature and date to the eCRFs as evidence thereof.

Access to the EDC system will be provided for the duration of the study through a password-protected method of internet access. Such access will be removed from investigator sites at the end of the site's participation in the study. Data from the EDC system will be archived on appropriate data media (e.g. CD-ROM) and provided to the investigator as a durable record of the site's eCRF data.

Original Questionnaires will be sent from the participating site to:

---

Confidential Information

### **9.6.2 Assignment of Preferred Terms**

AEs will be coded using the Medical Dictionary for Regulatory Activities (MedDRA) and will be tabulated by primary MedDRA system organ class (SOC) and preferred term (PT). For treatments, surgical and medical procedures the international non-proprietary name (INN) Drug Terms and Procedures Dictionary will be used.

## **9.7 Data Analysis**

### **9.7.1 Analysis Population, Time Windows and Handling of Missing Data**

The target population (TP) is defined as all patients who fulfill the criteria specified in Section 9.2.1. The core population (CP) is defined as all patients of the TP, who have started the treatment combination recommended in the current local label for their disease characteristics. Patients not receiving the treatment recommended in the local label will be summarized in the non-core population (NCP). In addition, the core population with sufficient follow-up data (CPSFU) is defined as all CP patients, who fulfil one of the following criteria:

- (1) evaluable HCV RNA data  $\geq 70$  days after the last actual dose of the ABBVIE REGIMEN (i.e. data within the SVR12 time window)
- (2) a HCV RNA value  $\geq 50$  IU/mL at the last measurement post-baseline (i.e. no virological response achieved at the last measurement on-treatment or post-treatment)
- (3) HCV RNA  $< 50$  IU/mL at the last measurement post-baseline, but no HCV RNA measurement  $\geq 70$  days after the last actual dose of the ABBVIE REGIMEN due to reasons related to safety (e.g. dropped out due to AE) or incomplete efficacy information (e.g. virologic failure such as relapse is reported in the eCRF but date and value of the corresponding HCV RNA test is missing). This means only patients who had virological response at their last on-treatment or post-treatment

---

Confidential Information

No use or disclose outside AbbVie is permitted without prior written authorization from AbbVie

---

measurement, but had no HCV RNA measurements  $\geq 70$  days post-treatment for reasons not related to safety or effectiveness (e.g. lost-to-follow-up or patient not willing to perform an additional HCV RNA test  $\geq 70$  days post-treatment) will be excluded from this analysis.

The Safety Population (SP) is defined as all patients who received at least one dose of the ABBVIE REGIMEN.

In accordance with the non-interventional nature of the study all HCV RNA measurements will be performed at the sole discretion of the physician and all HCV RNA measurements have to be entered into the eCRF. All recorded HCV RNA values will be assigned to appropriate time points (baseline, on-treatment visits, EoT visit, post-treatment visits). The time windows for the assignments will be specified in the statistical analysis plan (SAP).

No data will be imputed for any effectiveness or safety analyses except for the analyses of the HCV RNA endpoints. When there is no HCV RNA value in a visit time window post-baseline, but prior to EoT, the closest values before and after the window, regardless of the value chosen for the subsequent and preceding window, will be used for the flanking imputation described below. If a patient has a missing HCV RNA value at a post-baseline visit prior to EoT but has undetectable HCV RNA (with LLoD  $\leq 50$  IU/mL) or unquantifiable, but detectable HCV RNA levels (with LLoQ  $\leq 50$  IU/mL) at both the preceding and succeeding measurements, the HCV RNA level will be considered undetectable or unquantifiable, respectively, at this visit for this patient. In addition, if a patient has an unquantifiable HCV RNA level at the preceding measurement and an undetectable HCV RNA level at the succeeding measurement, or vice versa, the HCV RNA level will be imputed as unquantifiable at this visit for this patient. For virological response at EoT a corresponding backward imputation approach will be applied. This means if HCV RNA is missing at EoT, then unquantifiable or undetectable will be assumed for EoT, if the succeeding HCV RNA value is undetectable or unquantifiable. For SVR12 the single last available HCV RNA measurement  $\geq 70$  days post-treatment will be used. Subsequent to this flanking and backward imputation, if the HCV RNA value remains missing at a specific time point, then the patients will be considered as virological failure at this time point (i.e. not undetectable or unquantifiable).

### 9.7.2

### Demographics and Disease Characteristics

All baseline and disease characteristics will be summarized for the CP stratified by the CP analysis groups (i.e. based on genotype 1 subtype, fibrosis status, treatment

---

Confidential Information

No use or disclose outside AbbVie is permitted without prior written authorization from AbbVie  
The Netherlands v 1.4 (26 March 2018). Protocol based on AbbVie shell protocol version 3.0 (22 April 2015) Page 35 of 65

experienced or naive), which are relevant for scheduled treatment combination (ABBVIE REGIMEN  $\pm$  RBV) and duration (12 and 24 weeks). In addition, baseline summaries will be repeated for the SP and the TP without stratification into subgroups. Summary statistics (n, mean, median, standard deviation [SD] and range will be generated for continuous variables (e.g. age and body mass index [BMI]). The number and percentage of patients will be presented for categorical variables (e.g. gender). Further details of analysis populations and the CP analysis groups will be specified in the SAP, taking into account the ABBVIE REGIMEN recommended in the current local label for various patient groups.

### **9.7.3                   Effectiveness Analysis**

The primary effectiveness analysis on clinical outcomes will be performed on all patients in the CP stratified by the CP analysis groups. Due to the non-interventional nature of this study several different methods for determination of the HCV RNA value can be applied. For the purpose of the statistical analysis, a HCV RNA measurement is considered  $\leq 50$  IU/mL,

- if a PCR test was used
- and the test result is undetectable and the LLoD of the test is  $\leq 50$  IU/mL or the test result is unquantifiable and the LLoQ is  $\leq 50$  IU/mL

#### **9.7.3.1               Primary Effectiveness Endpoint**

The percentage of patients achieving SVR12 (single last HCV RNA  $<50$  IU/mL 12 weeks [i.e. at least 70 days] after the last actual dose of the ABBVIE REGIMEN) is the primary effectiveness endpoint.

#### **9.7.3.2               Secondary Effectiveness Endpoints**

The secondary effectiveness endpoints are:

- The percentage of patients with virological response (HCV RNA  $<50$  IU/mL) at EoT
- The percentage of patients with relapse (defined as HCV RNA  $<50$  IU/mL at EoT followed by HCV RNA  $\geq 50$  IU/mL)

---

Confidential Information

No use or disclose outside AbbVie is permitted without prior written authorization from AbbVie  
The Netherlands v 1.4 (26 March 2018). Protocol based on AbbVie shell protocol version 3.0 (22 April 2015) Page 36 of 65

- The percentage of patients with breakthrough (defined as at least one documented HCV RNA <50 IU/mL followed by HCV RNA ≥50 IU/mL during treatment).
- The number and percentage of patients meeting each and any of the following SVR12 non-response categories:
  - On-treatment virologic failure (breakthrough [defined as above ] or failure to suppress [each measured on-treatment HCV RNA value ≥50 IU/mL])
  - Relapse (defined as HCV RNA <50 IU/mL at EoT or at the last on-treatment HCV RNA measurement followed by HCV RNA ≥50 IU/mL post-treatment)
  - Premature study drug discontinuation with no on-treatment virologic failure
  - Missing SVR12 data and/or none of the above criteria

#### **9.7.3.3 Statistical Methods for Analysis of Effectiveness Variables**

The simple percentage of patients achieving SVR12 will be calculated and an exact two-sided 95% confidence interval (CI) of the percentage will be computed based on the Wilson's Score method.

Corresponding methods will be used for other response rates (EoT response rate, relapse rate, viral breakthrough). The relapse rates will be estimated in patients of the CP analysis groups with EoT response and sufficient HCV RNA measurements post-treatment. Viral breakthrough rates will be estimated in all patients of the CP analysis groups, who have at least one undetectable HCV RNA measurement on-treatment and at least one on-treatment or EoT measurement thereafter.

Univariate logistic regression methods will be used to investigate the impact of the following explanatory covariates on SVR12:

- Key demographic information
- Mode of CHC infection
- HCV RNA level at baseline
- Most recent stage of liver fibrosis
- HCV genotype and subtype (if available)
- Type of treating institute
- Liver and/or CHC related co-morbidities
- Key clinical chemistry and hematology laboratory variables at baseline

Confidential Information

No use or disclose outside AbbVie is permitted without prior written authorization from AbbVie  
The Netherlands v 1.4 (26 March 2018). Protocol based on AbbVie shell protocol version 3.0 (22 April 2015) Page 37 of 65

- In treatment experienced patients only:
  - Most recent prior treatment for CHC
  - Outcome of most recent prior CHC treatment

Further details and additional covariates will be specified in the SAP.

These analyses will be of exploratory nature, data driven, and will be repeatedly performed for various CP Analysis Groups, since not each covariate might be predictive in each patient group. Logistic regression methods will also be used to investigate the impact of treatment adherence on SVR12.

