4.2.5 Patient Disposition

The frequencies of patients belonging to the different populations (i.e. EP, TP, CP, CPSFU; SP) will be summarized by genotype and cirrhosis status and overall using the EP analysis groups as specified in section 4.2.1. The reasons for exclusion from a particular population will be also summarized in the frequency tables. Additionally, information on patient disposition will be listed.

Furthermore the frequency of patients not completing the study as defined per protocol (i.e. no HCV RNA assessment performed at least 10 weeks post-treatment), will be summarized by treatment regimen and cirrhosis status and additionally by genotype and cirrhosis status and overall for the SP and CP. The reasons for not completing the study as entered on the CRF will be displayed (i.e. failure to return, insufficient virological response (HCV RNA detectable at end of treatment, relapse post-treatment), patient never started treatment, withdrawn consent, death, other).

Additionally, the main reason for early termination of the ABBVIE regimen (AE or SAE [Physician decision], virological non-response [Physician decision], rebound or breakthrough [Physician decision], resistance to DAA [Physician decision], patient refused to continue treatment, patient withdrew consent to participate in the study, lost to follow-up, other, unknown [if actual duration is shortened for more than 7 days]) and Ribavirin (Anemia, Nausea/Vomiting, Rash, Other) will be summarized by treatment regimen and cirrhosis status and additionally by genotype and cirrhosis status and overall for the following different analysis populations: CP and SP.

Finally the study regimens assigned at baseline will be summarized (a) by genotype and cirrhosis status and (b) by genotype and pre-treatment status (treatment naïve vs treatment experienced) for CP and SP.

An overview of Tables is given in Table 5.

Table 5 Overview of Outputs for Patient Disposition

Output Title	Output Short Name	Analysis Population
Patient Disposition by Genotype and Cirrhosis Status – EP - <country>	tdis_<c>_gc_ep	Patients Enrolled
Listing of Patient Disposition - EP- <country>	ldis_<c>_ep	Patients Enrolled
Premature Termination of the Study and its Main Reason by <Treatment Regimen/ Genotype> and Cirrhosis Status - CP - <country>	tps_<c>_<t/g>c_cp	Core population

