4.2.7 Analyses of the Objectives

4.2.7.1 Primary Effectiveness Variable

The primary objective of this study is to estimate the SVR12 rates in HCV patients treated according to the ABBVIE regimen.

Therefore the simple percentage of patients achieving SVR12 (for definition see section 4.1.1) will be calculated and a two-sided 95% confidence interval (CI) of the percentage will be computed based on the Wilson's Score method.

The primary effectiveness analysis on clinical outcomes will be performed on all patients in the CP stratified by genotype and cirrhosis status and overall.

In the framework of sensitivity analyses the primary analyses will be repeated for the CPSFU. Furthermore, the SVR12 rates will be also determined for all patients of the NCP.

An overview of Tables is given in Table 7.

The layouts of the tables mentioned above are provided in Part II of the SAP (Table Shells).

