4.2.7.2 Secondary Variables

4.2.7.2.1 Secondary Effectiveness Variables

Response

For the other response rates (i.e. SVR24, EoT response rate, relapse rate, viral breakthrough), the simple percentage of patients and a two-sided 95% confidence interval (CI) of the percentage will be computed (based on the Wilson's score method) as well. The EoT response rates will be reported for CP and the SVR24 rates will be reported for the respective CPSFU, stratified by genotype and cirrhosis status and overall. The relapse rates will be estimated stratified by SVR window (i.e. during SVR12 window=relapse₁₂, during SVR24 window=relapse₂₄, after SVR24

window=relapse_{late}) and stratified by genotype and cirrhosis status and overall in patients of the CP with EoT response who fulfilled the following criteria:

- completed treatment as defined previously,
- had at least one HCV RNA measurement ≥ 70 days post-treatment or was a treatment failure between EoT and 70 days post-treatment.

Viral breakthrough rates [defined as at least one documented HCV RNA <50 IU/mL followed by HCV RNA ≥ 50 IU/mL during treatment] will be estimated overall and stratified by genotype and cirrhosis status in all patients of the CP, who have at least one undetectable or unquantifiable, on-treatment HCV RNA measurement and at least one on-treatment or EoT measurement thereafter.

Non-Response

In another table, the numbers and the percentages of the SVR12 non-responder categories and responder will be summarized for CP patients, overall and stratified by genotype and cirrhosis status. The following SVR12 non-response categories will be considered:

- On-treatment virologic failure (breakthrough [defined as at least one documented HCV RNA <50 IU/mL followed by HCV RNA ≥ 50 IU/mL during treatment] or failure to suppress [each measured on-treatment HCV RNA value ≥ 50 IU/mL])
- Relapse (defined as HCV RNA <50 IU/mL at EoT followed by HCV RNA ≥ 50 IU/mL post-treatment and completed treatment as defined previously)
- Death and none of the above
- Premature study drug discontinuation with no on-treatment virologic failure and none of the above
- Insufficient virological response, other than those mentioned above (patients for whom insufficient virological response was reported, or who had HCV RNA ≥ 50 IU/mL post EoT) and none of the above
- Missing SVR12 data and/or none of the above criteria

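### A virologic failure reported in the eCRF without an HCV RNA value fails SVR12 but cannot be a relapse or breakthrough event, and an early stop for declared breakthrough can be labelled as having no on-treatment virologic failure

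*Protocol*

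**What the plan says.** **SVR12 and the follow-up population.** Protocol 9.7.1 and SAP 4.2.1 keep in the core population with sufficient follow-up any patient whose "virologic failure such as relapse is reported in the eCRF but date and value of the corresponding HCV RNA test is missing". For SVR12, Protocol 9.7.1 states that "if the HCV RNA value remains missing at a specific time point, then the patients will be considered as virological failure"; SAP 4.2.3 has the same rule after imputation.

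**Relapse.** Protocol 9.7.3.2 and SAP 4.1.2 define it as a value below 50 IU/mL at EoT followed by a value of 50 IU/mL or more. On the denominator, Protocol 9.7.3.3 says "The relapse rates will be estimated in patients of the CP analysis groups with EoT response and sufficient HCV RNA measurements post-treatment". SAP 4.2.7.2.1 limits the rate to EoT responders who completed treatment and either have a measurement at least 70 days post-treatment or for whom the patient "was a treatment failure between EoT and 70 days post-treatment". It reports relapse by window: SVR12, SVR24 and later.

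**Breakthrough.** A documented value below 50 IU/mL followed by one of 50 IU/mL or more during treatment. The SAP denominator is patients with an undetectable or unquantifiable on-treatment value and any later on-treatment or EoT measurement.

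**Non-response categories.** Protocol 9.7.3.2 lists on-treatment virologic failure, relapse, "Premature study drug discontinuation with no on-treatment virologic failure", and missing or none of these. SAP 4.2.7.2.1 adds death and a category for other insufficient virological response, which accepts a reported failure. Categories from death downward each require that none above applies, and insufficient response stands below premature discontinuation.

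**Stop reasons.** SAP 4.2.5 tabulates reasons for early termination of the regimen that include "virological non-response [Physician decision], rebound or breakthrough [Physician decision".

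**The concern.** A report without a value is accepted as efficacy information when the follow-up population is defined, but not when relapse and breakthrough are counted. The same patient can therefore be a failure in the SVR12 table and be absent from the relapse rate, or sit in the breakthrough denominator as a non-event.

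The non-response table has a sharper problem. It is the table that explains why SVR12 was not reached, and it can state that no on-treatment virologic failure occurred in a patient whose recorded reason for stopping, shown in another table of the same report, is breakthrough or non-response. With few patients and probably few failures, one case can alter the account of why treatment failed.

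**Working it through.** The plan states no relapse or breakthrough rate, and the study size has no statistical basis, so there is no figure to reproduce. The check has two parts.

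**1. Tracing the patients through the rules**

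*Treatment completer, EoT response, relapse reported, no date or value, no later measurement.*
- SVR12: failure. Kept in the follow-up population.
- Relapse numerator: not met, because no value of 50 IU/mL or more exists. An undated event also fits none of the three relapse windows.
- Relapse denominator: under the Protocol, out unless the existing measurements are held sufficient. Under the SAP, in only through the treatment-failure clause, whose key term is undefined and whose day-70 limit cannot normally be checked without a date.
- Non-response table: insufficient virological response in the SAP, since SAP 4.2.5 includes post-treatment relapse under that reason. The patient stays in a virologic category there, but not in the relapse rate.

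*Patient stopped more than 7 days early for declared breakthrough, no value of 50 IU/mL or more recorded, no later measurement.*
- SVR12: failure.
- Breakthrough numerator: not met. Denominator: in, as a non-event, if any on-treatment or EoT measurement follows the first response value; otherwise out.
- Non-response table: on-treatment failure not met; relapse not met, as treatment was not completed; if alive, the next category is premature discontinuation with no on-treatment virologic failure. The category that would accept the report is never reached.
- Early-termination table (SAP 4.2.5): breakthrough.

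The last two lines contradict each other. A stop for virological non-response follows the same path when no on-treatment value was recorded.

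**2. Size of the effect on a rate**

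Inputs from the documents: "It is expected that 50-55 patients can be enrolled" (Protocol 9.5), and for SVR12 "a two-sided 95% confidence interval (CI) of the percentage will be computed based on the Wilson's Score method" (SAP 4.2.7.1), with the same method for the other rates. Assumptions: every enrolled patient is otherwise in the denominator, the reports are true, and there are r measured and k reported-only events.

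Let n be the denominator without the reported-only patients. Then

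(r+k)/(n+k) − r/n = k(n−r) / [n(n+k)],

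which is positive whenever r < n and k ≥ 1. If the patients stay in the denominator as non-events, the loss is k/(n+k).

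Wilson interval: [p + z²/(2n) ± z√(p(1−p)/n + z²/(4n²))] / (1 + z²/n), with z = 1.96.

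| N | r | k | Left out of both | Denominator only | Counted as events |
|---|---|---|---|---|---|
| 50 | 0 | 1 | 0/49 = 0.0% (0.0–7.3) | 0/50 = 0.0% (0.0–7.1) | 1/50 = 2.0% (0.4–10.5) |
| 50 | 1 | 1 | 1/49 = 2.0% (0.4–10.7) | 1/50 = 2.0% (0.4–10.5) | 2/50 = 4.0% (1.1–13.5) |
| 50 | 2 | 2 | 2/48 = 4.2% (1.2–14.0) | 2/50 = 4.0% (1.1–13.5) | 4/50 = 8.0% (3.2–18.8) |
| 55 | 0 | 1 | 0/54 = 0.0% (0.0–6.6) | 0/55 = 0.0% (0.0–6.5) | 1/55 = 1.8% (0.3–9.6) |
| 55 | 1 | 1 | 1/54 = 1.9% (0.3–9.8) | 1/55 = 1.8% (0.3–9.6) | 2/55 = 3.6% (1.0–12.3) |

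In the single-patient rows the loss is 1.8 to 2.0 percentage points. Example: n = 49, r = 1, k = 1 gives 48/(49 × 50) = 0.0196. With k = 0 nothing changes. Real denominators will be smaller than total enrolment, so the loss per patient would be somewhat larger.

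**The case against.** The best defence is that a measured value of 50 IU/mL or more is an objective criterion, used consistently in both documents. Protocol 9.9 stresses that sites use different assays whose limits must be documented. An undated report with no value cannot be checked against the threshold, so keeping it out of laboratory-defined numerators, while still failing the patient for SVR12, is defensible. That stands, and is why reported-only events belong in a sensitivity rate and not in the main one.

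The defence also limits how far the point goes. A reader might infer that such patients cannot enter these rates at all. The documents do not support this: the bar is on the numerators, a patient can sit in the breakthrough denominator, and the SAP's treatment-failure clause may admit some reported relapses. A reader might also infer that both rates are in fact understated. No count of such patients is given, the case appears only as an example within a population definition, and Protocol 9.7.1 requires every HCV RNA measurement to be entered. Nor is it right that reported failures vanish from the virologic categories in general: a completer's reported relapse is caught by the insufficient-response category. Calling premature discontinuation a tolerability category would be a gloss, since the SAP names no cause there, and the physician's reason is still shown in the early-termination table.

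None of this answers the category order. An explicit rule still produces a label that the recorded stop reason contradicts.

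**Conclusion.** The point holds in conditional form. If a virologic failure is reported without a value and no later value exists, the patient is an SVR12 failure who cannot be a relapse or breakthrough event. Each such patient would lower the affected rate by about 2 percentage points at 50 to 55 patients. This assumes that the report is true, that nearly all enrolled patients are in the denominator, and, for relapse, that the treatment-failure clause is not meant to count such reports. The number of such patients is unknown and may be zero, so no actual bias is shown. The intervals in the table overlap widely, and these are descriptive secondary rates.

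The mislabelling needs three things together: a stop more than 7 days early, breakthrough or non-response as the physician's reason, and no recorded value of 50 IU/mL or more. Where they meet, and the patient has not died, the SAP order gives a wrong label with certainty. A later value below 50 IU/mL, in or imputed into the SVR12 window, would make the patient a responder and remove the case. The SVR12 rate itself is not affected.

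**What to change.** In SAP 4.1.2 and 4.2.7.2.1, and in Protocol 9.7.3.2:

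1. Classify patients whose stop reason is rebound or breakthrough, or virological non-response, and who have no HCV RNA value that decides the matter, as reported on-treatment virologic failure. Rank this ahead of premature discontinuation. Where a deciding measured value exists, it prevails.
2. Keep the laboratory-defined relapse and breakthrough rates as the main rates. Add a sensitivity rate for each that counts reported-only failures in numerator and denominator; for relapse, pool all windows and show the date as unknown. Give the number of reported-only failures in a footnote.
3. Define what counts as a treatment failure between EoT and 70 days post-treatment, and say whether it counts as relapse or only admits the patient to the denominator.

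The cost is a few lines of text, some programming and one extra line per table; no new data are needed. The downside is that a few failures without laboratory confirmation may appear in the sensitivity rates and the category table, which the footnote makes visible.
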